# 6.5 Randomization and Timing of NasoVAX/Placebo

Subjects will be enrolled into 3 sequential cohorts of 20 subjects each defined by the viral particle dose  $(1\times10^9, 1\times10^{10}, \text{ or } 1\times10^{11} \text{ vp})$ . Within each sentinel group and cohort, subjects will be randomized at a ratio of 3:1 ratio to receive 1 intranasal dose of NasoVAX or placebo on Day 1.

A sentinel cohort of 5 subjects from each cohort will be dosed. Dosing of the remainder of each cohort may proceed after the last sentinel subject completes Day 8 if no events meeting stopping criteria (Section 6.6) have occurred. The SRC, consisting of the Investigator, the Medical Monitor, and a Sponsor Representative, will review all AE, reactogenicity, and laboratory data through Day 8 for all subjects in each cohort before subjects are randomized to the next higher dose.

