# 6.6 Stopping Criteria

If any event meeting the following criteria occurs, the SRC will review all available safety information before additional patients are dosed:

- Occurrence of any related SAE or Grade 4 AE
- Occurrence of 2 Grade 3 AEs in the same organ system
- Occurrence of the same Grade 3 laboratory abnormality in 2 or more subjects

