# 7.3 Reactogenicity (Diary)

Each subject will be provided with a diary and a thermometer after each dose. The subjects will record and provide severity grade (except for temperature) for the following items in a diary (sample provided in Appendix 2) and whether any medication or treatment was used for the symptom(s) daily for the first 14 days after dosing.

- Local events: nasal irritation, sneezing, nasal congestion, cough, sore throat, change in smell, change in taste, change in vision, eye pain
- Systemic events: headache, fatigue, muscle ache, nausea, vomiting, diarrhea, chills
- Oral temperature

If there are any events ongoing after the diary reporting period, these events will be followed until resolution and the stop date recorded. The Investigator (or Subinvestigator) will review the diary with the subject. Any changes or comments to the subject's diary by the Investigator (or Subinvestigator) must be made on the diary and initialed and dated by the Investigator (or Subinvestigator).

A reactogenicity event recorded on the diary will not be recorded as an AE unless it meets the criteria of an SAE.

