#### 9 ADVERSE EVENTS

#### 9.1 Definitions

#### 9.1.1 Adverse Event

An AE is any untoward medical occurrence in a patient or clinical investigation subject administered a pharmaceutical product and which does not necessarily have a causal relationship with this treatment. An AE can therefore be any unfavorable and unintended sign (including an abnormal laboratory finding), symptom, or disease temporally associated with the use of an IP, whether or not related to the IP.

The term AE is used to include any AE whether serious or nonserious.

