## 9.3 Recording of Adverse Events

An AE should be recorded individually in the study subject's own words (verbatim) unless, in the opinion of the Investigator, clarification of the subject's verbatim language is necessary or the AEs constitute components of a recognized condition, disease, or syndrome. In the latter case, the condition, disease or syndrome should be named rather than each individual symptom. The AE term will subsequently be coded using MedDRA.

The AE term, date of AE onset, date of AE resolution (if applicable), severity, causality, action taken for the AE, outcome and whether or not the AE is an MAE, NCI, and or SAE will be recorded.

05 October 2017 Confidential Page 40 of 66

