#### 12.7 Safety Analyses

The primary endpoint for evaluation of the safety profile is the number and percentage (95% CI) of subjects with solicited and unsolicited AEs recorded postvaccination. Safety analyses will be performed using the Safety Population.

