Nausea	None	No interference with daily activity	Some interference with daily activity	Prevents daily activity	So bad that required ER visit or hospitalization								
Vomiting	None	1-2 episodes past 24h OR No interference with daily activity	More than 2 episodes OR Some interference with daily activity	Prevents daily activity OR Requires outpatient IV hydration	So bad that required ER visit or hospitalization								
Diarrhea	None	2-3 loose stools past 24 h	4-5 stools past 24h	6 or more stools past 24h OR outpatient IV hydration	So bad that required ER visit or hospitalization								
Chills	None	Felt cold, mild shivering	Shaking chills 1-2 episodes	3 or more episodes of shaking chills	So bad that required ER visit or hospitalization								

Nasal Irritation	None	Not interfering with daily activity	Bothersome enough to interfere with daily activity or treated with medication	Severe enough to prevent daily activity	So bad that required ER visit or hospitalization
Sneezing	None	Not interfering with daily activity	Bothersome enough to interfere with daily activity or treated with medication	Severe enough to prevent daily activity	So bad that required ER visit or hospitalization
Nasal Congestion	None	Not interfering with daily activity	Bothersome enough to interfere with daily activity or treated with medication	Severe enough to prevent daily activity	So bad that required ER visit or hospitalization
Cough	None	Not interfering with daily activity	Bothersome enough to interfere with daily activity or treated with medication	Severe enough to prevent daily activity or interfere with breathing or eating	So bad that required ER visit or hospitalization
Sore Throat	None	Not interfering with daily activity	interferes with eating or other daily activity OR requires medication	Prevents daily activity OR requires narcotic medication	So bad that required ER visit or hospitalization
Change in Smell	None	Not interfering with daily activity	Bothersome enough to interfere with daily activity or treated with medication	Unable to distinguish odors even after decongestant medication	So bad that required ER visit or hospitalization
Change in Taste	None	Not interfering with daily activity	Affects enjoyment of meals or other interference with daily activity	Prevents ability to eat	So bad that required ER visit or hospitalization

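### The protocol contradicts itself on whether non-serious solicited diary events count toward the stopping criteria and the sentinel gate

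*Protocol*

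**What the plan says.** Section 6.6 requires SRC review before further dosing if any of three criteria is met. The first is a related SAE or any Grade 4 AE. The second is "Occurrence of 2 Grade 3 AEs in the same organ system". The third is one Grade 3 laboratory abnormality seen in at least two subjects. Sections 1.1 and 4.1 repeat the list. Reactogenicity is not named in any of the three places.

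Section 6.5 ties the sentinel gate to this list: "Dosing of the remainder of each cohort may proceed after the last sentinel subject completes Day 8 if no events meeting stopping criteria" were seen. It asks for no SRC review of sentinel data as such. The scheduled SRC review comes between cohorts, ahead of each escalation, where the committee "will review all AE, reactogenicity, and laboratory data through Day 8 for all subjects in each cohort before subjects are randomized" at the following dose level.

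On what an AE is, the protocol speaks in two ways:

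- Section 7.3, repeated in 9.5: "A reactogenicity event recorded on the diary will not be recorded as an AE unless it meets the criteria of an SAE".
- Section 9.1.1 defines an AE as "any untoward medical occurrence in a patient or clinical investigation subject administered a pharmaceutical product", whether or not causally related.
- Section 12.7 gives the primary safety endpoint as the "number and percentage (95% CI) of subjects with solicited and unsolicited AEs recorded postvaccination". The synopsis says the same.

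**The concern.** Solicited reactions are one of the two groups of primary safety endpoints in Section 3, and local reactions are a plausible dose-related toxicity of an intranasal spray. A stopping rule in a dose-escalation trial should say plainly whether they count. Here the answer depends on which section is read.

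Take two sentinel subjects in one cohort who each report a Grade 3 change in smell, which the Appendix 2 diary guideline describes as "Unable to distinguish odors even after decongestant medication". Section 2.4 reports that in animals the vector localised to the olfactory bulb, transiently and without inflammation or clinical observations. Suppose neither event is judged serious. Under 7.3 neither enters the AE record, no criterion in 6.6 is met, and 6.5 permits the other 15 subjects to be dosed without SRC review. Under 12.7 both are AEs, and if placed in the same organ system they meet the second criterion and dosing must pause.

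**Working it through.** **Text against text.** Four places bear on whether a non-serious diary event counts.

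1. Sections 7.3 and 9.5 address diary events by name and keep non-serious ones out of the AE record. This points to not counting.
2. Section 6.5 names AEs, reactogenicity and laboratory data as three kinds of data. Section 6.6 has criteria for two of them. This also points to not counting.
3. Sections 9.1.1 and 12.7 point to counting. So does 9.4.1, which grades AEs by Appendix 1, a scale that includes fever, headache, fatigue, myalgia, nausea/vomiting and diarrhea, all of them solicited items.
4. Section 6.6 does not say which sense of AE it uses.

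The more specific text excludes these events, the more general text includes them, and nothing settles the conflict.

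**What falls in the gap on the 7.3 reading.**

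- Grade 3: every non-serious diary event.
- Grade 4: the diary grade is an ER visit or hospitalization. Inpatient admission is an SAE under 9.1.4, so it is recorded as an AE and can meet the first criterion. What remains is, for example, an ER visit without admission that is not judged serious.

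**Who is affected.** Section 3 lists 9 local and 8 systemic solicited items, 9 + 8 = 17. Each cohort has 20 subjects and 5 sentinels, so 3 × (20 − 5) = 45 subjects are dosed after the gate, and 45/60 = 75%. Five subjects do not split exactly 3:1, so I assume 3 or 4 sentinels per cohort on NasoVAX. Of the 45, NasoVAX then goes to 45 − 3 × 4 = 33 up to 45 − 3 × 3 = 36.

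**The protocol's own figures.** Section 12.9 gives no operating characteristic for the stopping criteria. Its two safety figures do reproduce: 1 − (1 − 0.036)^45 = 0.808 against the stated 80%, and 1 − 0.10^(1/45) = 4.99% against the stated 5%. The point does not rest on them.

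**Illustration.** The protocol gives no Grade 3 solicited rate. Assume a per-recipient rate p for Grade 3 events in one organ system, and ignore placebo recipients. Then

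P(at least 2 of n affected) = 1 − (1 − p)^n − n·p·(1 − p)^(n − 1)

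For n = 15 and p = 0.10 this is 1 − 0.206 − 0.343 = 0.451. In full:

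| Assumed p | n = 3 active sentinels | n = 4 active sentinels | n = 15 NasoVAX in the cohort |
|---|---|---|---|
| 5% | 0.7% | 1.4% | 17.1% |
| 10% | 2.8% | 5.2% | 45.1% |
| 20% | 10.4% | 18.1% | 83.3% |

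These are chances that two or more subjects are affected. They are not the probability of meeting the second criterion, which counts AEs: one subject with two Grade 3 events in the same organ system could meet it. The whole-cohort column also overstates useful pauses, because a pause after the last dose protects no one. On the 7.3 reading, non-serious diary events contribute nothing to any criterion, whatever p is.

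**Cohort 3.** The scheduled reactogenicity review precedes the next higher dose, and after 1×10^11 vp there is none. The highest earlier intranasal dose in Section 2.6 is 3.3×10^9 vp, and 1×10^11 / 3.3×10^9 is about 30. For the 15 post-sentinel subjects of this cohort, the criteria in 6.6 are the only formal trigger for review while dosing continues.

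**The case against.** The best reply is that 7.3 and 9.5 only say where an event is captured, so that it is not entered twice. Section 6.6 is triggered when AEs occur, not when they are recorded; 9.1.1 is broad; 12.7 calls diary events AEs. On that reading solicited reactions are AEs held in the diary, and they count. The reading is possible, and for that reason a reader should not infer that severe solicited reactions are definitely outside the stopping rule. But 6.5 separates reactogenicity from AEs and 6.6 is silent, so the reply establishes an ambiguity and does not resolve it.

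Other safeguards are real. The investigator reviews the diary at the Day 2 call and on Days 4 and 8, before the gate opens, and sits on the SRC. The gate is permissive, so an ad hoc hold is open. Section 9.1.4 lets important medical events be judged serious and sends doubtful cases to the Medical Monitor. Under 9.5, clinically significant examination and vital-sign findings become AEs. These narrow the gap but rest on judgement, and a subjective loss of smell or taste may leave no finding on examination.

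Two further inferences should not be drawn. One is that Grade 4 diary events escape generally; only those not judged serious do. The other is that diary events cannot be assigned to an organ system because coding is specified for AE terms ("The AE term will subsequently be coded using MedDRA", Section 9.3). Section 6.6 says organ system without reference to that dictionary, and nasal congestion or cough can be placed without coding.

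Earlier studies in Section 2.6 found mostly mild reactions, which argues for low rates. The intranasal doses there were similar to the lowest dose here or lower, so they do not settle the rate at 1×10^10 or 1×10^11 vp.

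**Conclusion.** The contradiction stands and is worth correcting; it is a point to consider, not a fatal flaw. The protocol does not settle whether non-serious solicited events count toward 6.6 and the sentinel gate. On its more specific wording they do not, and no hold within a cohort is then required for non-serious Grade 3 diary events or for Grade 4 diary events not judged serious.

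A reader might go further and conclude that dose escalation itself ignores reactogenicity. It does not: the reviews before cohorts 2 and 3 include it. The exposure is dosing at the same dose level within a cohort, and it matters most in cohort 3. The counts of subjects follow from the design, with 3 or 4 active sentinels per cohort assumed; the event rates are assumptions throughout.

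**What to change.** In 6.6 and its copies in 1.1 and 4.1, state that Grade 3 or higher solicited events recorded on the diary count toward the criteria. If the sponsor wants to tolerate expected local reactions, give solicited events their own threshold instead, for example the same Grade 3 solicited event in two or more subjects. In 6.5, state that the sentinel check includes diary data through Day 8. In 12.7 and the synopsis, change the endpoint wording to *solicited events and unsolicited AEs*, so that it agrees with 7.3. Keeping diary events out of the AE record can stay as it is.

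The cost is a few sentences. No new data are needed, since diaries are already reviewed on Days 2, 4, 8 and 15. The downside is somewhat more pauses for SRC review, which a separate threshold would limit.

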# 7.4 Adverse Events (Including Medically Attended Events, Serious Adverse Events, and New-onset Chronic Illnesses)

See Section 9.

# 7.5 Height and Weight

Height and weight will be measured and recorded at Screening.

# 7.6 Complete Physical Examination

Examination of the following systems will be performed at the time points specified in the Schedule of Events and as clinically indicated: cardiovascular; dermatological; head, eyes, ear,

05 October 2017 Confidential Page 32 of 66

nose, and throat; extremities; gastrointestinal; musculoskeletal; neurological ophthalmological; neurological; respiratory.

Any clinically significant change in physical examination finding will be recorded as an AE (see Section 9.5).

# 7.7 Targeted and Symptom-driven Physical Examination

Examination of the respiratory and head, eyes, ear, nose, and throat systems and any additional systems as indicated by signs or symptoms reported by the subject will be performed at the time points specified in the Schedule of Events and as clinically indicated. An otorhinoscopic examination and visual examination of the nasopharynx will be conducted with findings recorded on a structured evaluation form.

Any clinically significant change in physical examination finding will be recorded as an AE (see Section 9.5).

# 7.8 Vital Signs

At the time points specified in the Schedule of Events and before any blood sample collection, systolic and diastolic blood pressure and pulse will be measured and recorded using a semiautomatic recording device with an appropriate cuff size after the subject has been in a supine position for at least 5 minutes. Oral temperature will also be measured. Any clinically significant abnormal vital sign value will be recorded as an AE (see Section 9.5).

# 7.9 Electrocardiogram

At the time points specified in the Schedule of Events and before any blood sample collection, a 12-lead ECG will be performed after the subject has been in a supine position for at least 5 minutes. Interpretation (normal, abnormal not clinically significant, abnormal clinically significant) will be recorded. Any clinically significant change in ECG interpretation will be recorded as an AE (see Section 9.5).

# 7.10 Blood Samples

# 7.10.1 Safety Laboratory Tests

Samples for the following tests will be collected, processed, and shipped to the laboratory in accordance with instructions in the laboratory manual at the time points specified in the Schedule of Events:

- Hematology: hemoglobin, platelet count, white blood cell count with differential (absolute or percent counts of neutrophils, lymphocytes, monocytes, basophils, eosinophils)
- Serum chemistry: alkaline phosphatase, ALT, AST, bicarbonate, bilirubin, chloride, creatine kinase, creatinine, glucose, potassium, sodium, urea nitrogen
- Urinalysis: glucose, protein

05 October 2017 Confidential Page 33 of 66

Any laboratory abnormality deemed clinically significant by the Investigator should be recorded as an AE (see Section 9.5).

# 7.10.2 Serum Samples (Immunogenicity)

Serum samples will be collected and processed at the time points specified in the Schedule of Events. Collection, processing, labelling, storage and shipping instructions for these samples are provided in the laboratory manual.

Influenza virus HAI assay against A/California/04/2009(H1N1) will be performed on all samples collected.

Ad5 microneutralization, influenza microneutralization against all strains, and HAI against nonrepresented strains will be performed on samples collected on Days 1 and 29 only. A larger serum sample will be collected on Days 1 and 29 for these assays.

# 7.10.3 Peripheral Blood Mononuclear Cells (Immunogenicity)

Whole blood samples will be collected and processed to isolate PBMCs at the time points specified in the Schedule of Events. Collection, processing, labelling, storage, and shipping instructions for these samples are provided in the laboratory manual.

ELISpot will be performed on all samples for measurement of T-cell activity.

# 7.11 Pregnancy Tests

A serum or urine sample will be collected from all women who have not been surgically sterilized or have laboratory confirmation of postmenopausal status and tested at the time points specified in the Schedule of Events.

# 7.12 Nasopharyngeal Swabs

A nasopharyngeal swab sample will be collected and processed at the time points specified in the Schedule of Events. Collection, processing, labelling, storage, and shipping instructions for these samples are provided in the laboratory manual. Nasopharyngeal swabs are not obtained on the day of dosing in order not to disturb the nasal mucosa. A qPCR assay for detection of the RD vector will be performed on swab samples to measure concentration of the RD vector. Once a negative result is obtained, later samples may not be tested. Screening and Day 29 samples will also be tested for influenza IgA by ELISA.

#### 7.13 Viral Culture

A sample (as clinically indicated) for viral culture will be collected from any subject who experiences acute symptoms compatible with possible adenoviral infection within 28 days after the NasoVAX/placebo dose. The sample will be collected, processed, and shipped to the laboratory in accordance with instructions in the laboratory manual.

05 October 2017 Confidential Page 34 of 66

# 8 STUDY VISITS

# 8.1 Screening (Within 28 Days Before Day 1)

The subject will be screened to assess eligibility criteria. The following assessments and procedures will be performed:

- Written informed consent
- Demographics
- Medical history
- Concomitant medications (including vaccines) recording
- Complete physical examination
- Height and weight
- ECG
- Vital signs
- Drug and alcohol screen
- Collection of laboratory samples:
  - o Hepatitis B and C and HIV tests
  - o Clinical laboratory tests (hematology, serum chemistry, urinalysis)
  - Serum pregnancy test
  - Nasopharyngeal swab

# 8.2 Dosing Period

If at any time in the Dosing Period (Days 1 to 29) the subject experiences acute symptoms compatible with adenoviral infection, a sample for viral culture will be collected.

# 8.2.1 Day 1

The following procedures will be performed before NasoVAX/placebo administration:

- Concomitant medications (including vaccines) recording
- AE assessment
- Complete physical examination
- Vital signs
- Drug and alcohol screen
- Urine pregnancy test

- Sample collection:
  - Serum for humoral response (including serum for additional assays [see Section 7.10.2 and the laboratory manual for details])
  - o Whole blood sample for isolation of PBMCs for cellular response
- Eligibility criteria check

Upon determination that a subject meets all eligibility criteria, the subject will be **randomized** to treatment assignment (as described in Section 6.5) and NasoVAX/placebo administered. The subject will be instructed not to blow his/her nose for 30 minutes after dosing.

The following procedures will be performed 2 hours after NasoVAX/placebo administration:

- Targeted and symptom-driven physical examination
- Vitals signs

Before discharge from the unit, the subject will be given a diary and instructed to record temperature, local events, and systemic events at the same time today and each day and whether any medication or treatment was used for the symptom(s) for the next 14 days. The subject will also be instructed that, if any event is ongoing for more than 14 days after the dose, to follow the event until resolution and report the stop date. The subject will be instructed to bring the diary back to the unit at the next visit.

Before discharge from the unit, the following procedures will also be performed.

- Concomitant medications recording
- AE assessment

# 8.2.2 Day 2 (Telephone Contact)

The following procedures will be performed:

- Review of diary
- Concomitant medications (including vaccines) recording
- AE assessment

# 8.2.3 Day 4 (± 1 Day)

The following procedures will be performed:

- Review of diary
- Targeted and symptom-driven physical examination
- Vitals signs
- Concomitant medications (including vaccines) recording
- AE assessment

05 October 2017 Confidential Page 36 of 66

- Sample collection:
  - o Serum for humoral response
  - Nasopharyngeal swab

#### 8.2.4 Day 8 (± 1 Day)

The following procedures will be performed:

- Review of diary
- Targeted and symptom-driven physical examination
- Vitals signs
- Concomitant medications (including vaccines) recording
- AE assessment
- Sample collection:
  - o Clinical laboratory tests (hematology, serum chemistry, urinalysis)
  - Serum for humoral response
  - Whole blood sample for isolation of PBMCs for cellular response
  - Nasopharyngeal swab

